## 1. Objectives

Our long-term goal is to develop safe and effective treatments for symptoms of mild to moderate TBI (mmTBI) that restore patients to higher levels of functioning, decrease disability, and promote brain healing. The objective of this application is to investigate the use of transcranial direct current stimulation (tDCS) to treat symptoms of executive dysfunction and depression in patients with mmTBI. Our central hypotheses are (1) tDCS paired with relevant cognitive training facilitates improves executive function on NIH-approved neuropsychological measures, (2) tDCS reduces depression scores on NIH Common Data Elements for TBI, (3) that these improvements in emotion and cognition will be detectable up to one year after stimulation, (4) (4) certain clinical variables will reliably predict response to tDCS, such as age, education level, injury severity, and magnetic resonance imaging (MRI) evidence of structural/functional/metabolic abnormalities and (5) quantitative electroencephalography (EEG) will demonstrate changes in frontal midline theta band power and theta band synchrony, markers of cognitive control, in responders. These objectives were formulated based on our clinical experience with [name] (project mentor) characterizing symptomatic patients with mmTBI in the post-acute setting, groundbreaking research led by [name] (project mentor) that has demonstrated robust increases in attention and learning with tDCS, and extensive evidence accumulated by co-junior investigator on the grant application [name] on EEG measures of executive dysfunction.

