### Specific Aim 1: tDCS for executive dysfunction in mmTBI

Experiments in this aim will test the hypothesis that in patients with mmTBI, left prefrontal anodal tDCS concurrent with cognitive training for up to ten consecutive weekdays will result in significantly more improvement in executive function compared to sham stimulation. Patients with cognitive complaints 3 months to 15 years after mmTBI will be recruited from local emergency departments and brain injury clinics. Healthy controls will also be recruited through flyers, advertisements and word of mouth. Aim 1.1: tDCS will be paired with computer-based cognitive training tasks of response inhibition, set shifting, and working memory, while executive function will be measured with the NIH Examiner battery before, immediately after, and one month after stimulation. Pre-and post-stimulation EEG and MRI may be obtained. During EEG and MRI participants may be asked to rest quietly or perform simple tasks. Aim 1.2: Persistence of post-traumatic symptom reduction and quality of life improvement will be assessed with Common Data Elements instruments via telephone interview at 6 months and one year. Aim 1.3: Clinical predictors of tDCS response including EEG frontal theta synchrony, injury severity, presence of neuroimaging abnormalities, premorbid intelligence, and post-traumatic symptom burden will be determined with linear mixed-models analysis.

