### Review of relevant literature

*tDCS can improve brain function.* Anodal tDCS typically has an excitatory neuronal effect due to a shift toward depolarization, while cathodal stimulation elicits a hyperpolarization. tDCS-induced changes last from minutes to hours, and multiple stimulation sessions over the course of days to weeks can lead to cumulative long-lasting effects. This powerful neuroplastic effect of tDCS has

PROTOCOL TITLE: Transcranial direct current stimulation for treatment of deficits after traumatic brain injury.

already been applied to injured brain in patients recovering from stroke, with observed benefits in motor control, neglect, vision, and aphasia, without adverse consequences such as seizures or worsening of deficits. Anodal stimulation of the dorsolateral prefrontal cortex (DLPFC) has become a standard protocol in the cognitive tDCS literature because of its ability to improve multiple dimensions of cognitive functioning, including cognitive control and working memory, attention, improved decision making, and enhanced memory. Reduction of impulsivity has been demonstrated with anode over right DLPFC.

*tDCS is understudied in TBI.* Application of this therapy to TBI is a logical next step, but tDCS has not been extensively studied in this disorder as it has for stroke rehabilitation and depression. Several animal studies have shown that anodal tDCS is potentially neuroprotective after brain injury. Only three studies have attempted tDCS for cognition in TBI, all utilizing left prefrontal anodal stimulation. Angelakis et al. treated 5 severe TBI patients with 5 days of anodal 1 mA tDCS for 20 minutes then 5 days of 2 mA. Age of injury ranged from 6 months to 10 years, and electrode positioning was at left DLPFC or left sensorimotor cortex (C3) in alternating order. There were no adverse events, and no clear advantage from either electrode position. Three patients of the five experienced benefit by 1 year followup.

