#### Experimental Design and Methods

*Participants:* TBI subjects enrolled in Aim 1.1 will be entered into a data registry with comprehensive contact information, including contact information (phone, email, fax, mail address) not just on participants, but also on multiple collaterals we can contact for 6 month and 1 year assessments.

*Assessments:* Initial screening will be done prior to tDCS intervention, and will be performed verbally to resemble subsequent phone interviews. These assessments will include the Neurobehavioral Symptom Inventory (NSI), and the PROMIS-29 quality of life profile. Dimensions queried by the PROMIS-29 survey will include physical function, anxiety, depression, fatigue, pain, sleep, and social roles. At 6 months and 1 year after the end of stimulation, subjects will be contacted by phone by the research team for a brief assessment of their post-traumatic symptoms and quality of life. Subjects not able to be contacted by phone will be sent a letter with the surveys in paper form to be returned via mail, fax, or email.

Specific Aim 1.3: Clinical predictors of tDCS response

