### Specific Aim 2.2:

The subjects from Aim 2.1 will be automatically included. At 6 months and 1 year after stimulation, subjects will be contacted via telephone and administered the depression assessment tools utilized before, immediately after, and 1 month after stimulation.

**Specific Aim 2.3:** Subjects from Aim 2.1 will be carried forward for study in Aim 2.3. Patient and injury characteristics will predict positive response to tDCS, namely, higher premorbid intellectual function (WTAR), lesser severity of injury (mild versus moderate), lack of neuroimaging abnormalities on MRI, and more severe pre-stimulation depressive symptoms (BDI, HAM-D). Understanding which of the clinical variables described above moderate the efficacy of tDCS in mmTBI will allow for more precise patient selection and better overall efficacy in future applications.

Each of the 80 participants will receive \$20/hr in the form of cash cards for taking part in the study.. This is felt to be a fair amount that is not coercive and will help decrease attrition for this study which involves many visits.

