
## 12. Provisions to Monitor the Data to Ensure the Safety of Subjects

Data safety and monitoring will be carried out to ensure and maintain the scientific integrity of this project and to protect the safety of our participants. Safety monitoring is the process during the study that involves review of accumulated outcome data for groups of subjects to determine if any of the procedures practiced should be altered or stopped. Ultimately, the PI ([name]) will be responsible for monitoring the safety of the study and complying with the reporting requirements. An independent Data Safety and Monitoring Board (DSMB) will review the study data on a quarterly basis with the PI to ensure participant safety. The DSMB for this study will be composed of [name], the medical director of the Electroconvulsive Therapy Service at UNM, and [name], staff epileptologist of the Epilepsy Monitoring Unit at UNM. Their experience in assuring safety of brain stimulation therapies and seizure monitoring protocols make them ideally suited to serving on this project's DSMB. Continuous, close monitoring of participant safety will include prompt and frequent reporting of safety data (i.e., adverse/serious adverse events) to the

**PROTOCOL TITLE:** Transcranial direct current stimulation for treatment of deficits after traumatic brain injury.

DMSB, the University of New Mexico Health Sciences Center Institutional Review Board (UNMHSC IRB) and/or appropriate NIH staff with oversight responsibility. The PI will provide a summary of the safe conduct of the study to NIH on an annual basis as part of the progress report. All AEs occurring during the course of the study will be collected, documented, and reported to the UNMHSC IRB.

The review of data may result in early termination of the study, amendment to the protocol, or changes to the data collection plan or study forms if it appears that there are adverse events occurring at a rate significantly greater than that found in similar tDCS studies involving subjects with neurological disorders (ie. stroke). Should the protocol or data collection plans or study forms be amended as a result of data review, the IRB will be notified and the amendment approved prior to study amendment implementation. In addition, the participants will be notified of any significant new findings that develop during the course of research that may affect their wish to continue participation in the study.

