We have extensive experience using 11 cm^2 sponges with 2.0 mA for 30 minute sessions, with excellent tolerability of skin sensation, and effective blinding of stimulation. The use of 35 cm^2 sponges spreads stimulation over a significantly larger area and reduces efficacy to achieve cortical excitability. Given that our patient population is an outpatient, ambulatory, mild to moderate TBI population and that these current strengths and amounts have already been administered safely to patients with stroke and TBI lesions ipsilateral and proximal to the site of stimulation, we feel these parameters are extremely safe. Our group is currently studying tDCS in subjects with tobacco use disorder, alcohol use disorder, and schizophrenia and are finding the stimulation to be very safe and well tolerated. To date, 138 subjects have undergone published tDCS protocols with our group and only two subjects withdrew because of intolerable sensations. We find that about 1% of subjects on the average can't tolerate the skin stimulation caused by tDCS (heat, itching or burning sensations) and so we stop for them. The other 99% tolerate it well. We had one case of a system with a small piece of bare wire that touched the skin and caused a skin burn, which was small but needed attention. This can be avoided by having a tDCS setup with fully insulated wiring.

A Data Safety and Monitoring Board will review study data with the PI quarterly for any side effects or adverse events. The device will be kept behind locked doors at all times at the Clinical Core of the Center when not being used expressly for the current study. The principal investigator and trained research personnel will be the only persons with access to the device.

There are no long term neuropsychiatric effects from tDCS. With repeated stimulation, some subjects get dry skin. Applying lotion helps to ameliorate this. Using EEG gel rather than saline for the electrode conductor helps reduce this occurrence as well.

The TDCS device is determined to be a Non-Significant Risk device by the sponsor-investigator ([name]) for the following reasons:

- 1) It is not intended as an implant
- 2) It does not present a potential for serious risk to the health, safety, or welfare of the subjects
- 3) It is not proposed to be for a use in supporting or sustaining human life

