- 4) It is not for a use of substantial importance in diagnosing, curing, mitigating, or treating disease, or preventing impairment of human health

According to the FDA, serious adverse events are those in which the outcome is death, life-threatening, hospitalization, disability/permanent damage, congenital anomaly, requiring intervention to prevent permanent impairment, or other serious events such as refractory seizures, cardiorespiratory arrest, or anaphylactic reaction. No serious adverse events attributable to TDCS have been reported in the more than 10,000 subjects investigated in the contemporary TDCS literature since 1998. This literature includes studies in patients with severe brain injury, stroke, epilepsy, and neurodegenerative disorders, none of whom have been reported to experience serious adverse events. Specifically, there have been no reports or evidence presented of damage to the brain, seizures, or cardiorespiratory arrest. Animal studies of charge densities necessary to induce brain damage in rats were found to be 100 times higher than the charge density used in TDCS trials with standard parameters (< 2.5 mA, no more than 2 sessions daily, < 60 min per session, use of electrodes that minimize skin burns) as determined by world-wide expert consensus. The commonly reported side effects of TDCS are itching, burning, tingling, headache, and discomfort (10-40%), all of which are mild and transient. As this trial will be operating within standard parameters as defined

PROTOCOL TITLE: Transcranial direct current stimulation for treatment of deficits after traumatic brain injury.

above, we believe our use of TDCS in subjects with mild-moderate traumatic brain injury represent a Non-Significant Risk.

PROTOCOL TITLE: Transcranial direct current stimulation for treatment of deficits after traumatic brain injury.

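### The plan promises to collect all adverse events for up to a year, but the 1-, 6- and 12-month contacts as described contain no adverse-event question, so late discrete events rest on volunteered report

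*Combined protocol and SAP*

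**What the plan says.** **Collection promised.** Section 12 states "All AEs occurring during the course of the study will be collected, documented, and reported to the UNMHSC IRB". Section 3 says an individual's participation may run to one year.

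**Checks around stimulation.** Section 10 (safety of stimulation), repeated in section 13, has participants rate skin sensations, mood, energy, pain and arousal every ten minutes during a session. The Aim 2.1 stimulation protocol adds a mood rating before and after each session. Section 16 repeats the discomfort rating.

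**Contacts after stimulation.**
- One month: the EXAMINER battery (Specific Aim 1, section 1) and the depression assessments (Aim 2.1, section 10).
- Six and twelve months, Aim 1.2: "subjects will be contacted by phone by the research team for a brief assessment of their post-traumatic symptoms and quality of life", using the NSI and PROMIS-29. Section 1 frames this aim as "Persistence of post-traumatic symptom reduction and quality of life improvement will be assessed with Common Data Elements instruments via telephone interview".
- Six and twelve months, Aim 2.2: "subjects will be contacted via telephone and administered the depression assessment tools" used at the earlier visits.

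**Safety wording.** Section 31 says "There are no long term neuropsychiatric effects from tDCS". Section 1 hypothesises "that these improvements in emotion and cognition will be detectable up to one year after stimulation", and the literature review says "multiple stimulation sessions over the course of days to weeks can lead to cumulative long-lasting effects". Section 31 ends its description of serious events with "or other serious events such as refractory seizures, cardiorespiratory arrest, or anaphylactic reaction", then says that the literature contains no reports of seizures, without the word refractory.

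**The concern.** An event has to be asked about, measured or volunteered to enter the database. Once stimulation ends, the plan names measuring scales but no AE question. A seizure, an episode of elevated mood, a new neurological diagnosis or a hospital stay in the following year would be recorded only if the participant raised it. The commitment in section 12 would then have no described procedure behind it for most of each TBI participant's time in the study.

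This affects how the results can be read. A report of no late events could not distinguish absence of events from absence of questions. Section 12 also allows the trial to be stopped or amended if AEs run above the rate in similar tDCS studies, and under-reporting lowers the rate that enters that comparison. Both TBI arms are already being telephoned, so the chance to collect these events in a randomized comparison would be lost with almost nothing saved.

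**Working it through.** The plan gives no figure for late harm, so the main check sets passages side by side. Arithmetic then sizes what the scales and an AE query could each show.

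**1. What each later contact can capture**

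| Contact | Content described | Can show worsening on a scale? | AE question described? |
|---|---|---|---|
| 1 month | EXAMINER battery, BDI-II, HAM-D | Yes | No |
| 6 and 12 months, Aim 1.2 | NSI, PROMIS-29 | Yes | No |
| 6 and 12 months, Aim 2.2 | Depression tools as before | Yes | No |

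The procedure table in section 20 lists three neuropsychological tests and two telephone interviews and has no AE entry. Section 16 reports several hypomania cases in earlier tDCS studies. The monitoring precautions it lists are mood ratings during stimulation and depressive questionnaires before and after treatment, neither described as measuring elevated mood. It also relies on excluding patients who take psychotropic medication, whereas the inclusion criteria admit patients on stable doses; those two passages must be reconciled.

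**2. What the scales can show**

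Section 11 compares groups over five time points on the NSI cognitive-items score and the PROMIS-29 total. It claims 80% power for 40 against 40 at d = 0.7 and states neither alpha nor sidedness.
- Noncentrality: 0.7 × √(40/2) = 3.130.
- Two-sided alpha 0.05 (assumed): Φ(3.130 − 1.960) = 0.879; exact t, 0.871.
- Two-sided alpha 0.025 (assumed): Φ(3.130 − 2.241) = 0.813; exact t, 0.799, which matches the plan's 80%.

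By symmetry, power against worsening of d = −0.7 is the same. A lasting deterioration as large as the assumed benefit is therefore as detectable as the benefit. Two limits apply: sections 11 and 14 do not name BDI-II or HAM-D as one-year dependent variables, and neither section plans any AE tabulation by arm.

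**3. What a structured query could show**

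Inputs: 40 active TBI patients (section 10, Participants), and full follow-up to one year (assumed).
- Zero events, one-sided 95% upper bound: 1 − 0.05^(1/40) = 0.072.
- Probability of at least one event, 1 − (1 − p)^40: 33% for p = 1%, 55% for p = 2%, 87% for p = 5%. These values of p are assumed.

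Aim 1.2 names only TBI subjects for long-term follow-up. If all 80 active participants, healthy controls included, were followed, the zero-event bound would be 1 − 0.05^(1/80) = 0.037.

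**4. What volunteered report can show**

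If a fraction s of events is volunteered, zero reports bound s × p, not p. The bound on the true rate becomes 0.072/s. The documents give no basis for s, so zero reports would give no usable bound.

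**The case against.** The strongest reply is that late harm is already covered. The NSI, PROMIS-29 (which includes anxiety, depression, fatigue, pain and sleep), BDI-II and HAM-D move in both directions, and section 11 tests group differences, not improvement alone. Suicidal ideation at any assessment triggers evaluation under Aim 2.1. Section 12 requires all AEs to be collected, and a safety board reviews data quarterly. The plan's silence on how AEs are elicited does not prove that nobody will ask. The section 31 sentence sits among remarks on side effects and most naturally means no lasting adverse effects, so its conflict with a hypothesis of lasting improvement is largely one of wording.

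Most of this stands. A reader might infer from the benefit-framed aims that the late contacts ask only about benefit, so that the trial can show lasting benefit but not lasting harm. The documents do not support that, because the instruments register worsening. Nor do they support saying that AEs are excluded after treatment.

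The reply does not reach discrete events. No named scale is described as covering seizure or mood elevation, and a general promise to collect AEs does not say who asks, what or when. A form outside the document may contain the question; if so, the plan should say so.

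A reader might also infer from section 31 that a seizure that is not refractory would count as non-serious. The list is illustrative, and a life-threatening event or one leading to hospitalization qualifies under its earlier terms. The two references to seizures need reconciling, and no seriousness rule follows from them.

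**Conclusion.** The point holds in a limited form. Followed as written, the contacts at 1, 6 and 12 months contain no AE enquiry and no instrument described as covering seizure or hypomania. Late discrete events therefore depend on volunteered report, and no table by arm is planned for them. Lasting worsening on the symptom, mood and quality-of-life scales can be seen, so the gap concerns events and not harm in general.

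The gap spans about a year per TBI participant after a stimulation course of up to ten weekdays. Closing it would let a zero count in 40 active patients bound the one-year rate at 7.2%, assuming full follow-up, with 40 sham patients as comparator. It would not settle rare harms: at a true rate of 1% the trial would more likely than not see no event in the active arm (1 − 0.33 = 0.67).

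The unqualified sentence in section 31 needs correcting, but rewording it alone would change nothing that the trial does.

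**What to change.** 1. Add a short structured AE query to the 1-month visit and to the 6- and 12-month contacts, including the paper version sent to participants who cannot be reached by phone. Ask about any seizure, any episode of elevated mood or other new psychiatric episode, any new neurological diagnosis and any hospitalization.
2. Specify that the person asking does not know the arm. Aim 1.2 says only that the research team makes the contact, and section 10 leaves the study coordinator unblinded.
3. Add to section 11 a table of these events by randomized arm to one year, with the number asked at each contact as denominator. State whether healthy controls are followed.
4. Qualify the section 31 sentence, for example by saying that long-term effects are not established and are under study here, so that it agrees with section 1 and the literature review.
5. Reconcile the references in section 31 to refractory seizures and to seizures, so that a reader knows which is meant in each place.

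The cost is a few minutes per existing contact, one case report form page, one table and a wording amendment. No new visit or procedure is needed.

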## Checklist Section

This section contains checklists to provide information on a variety of topics that require special determinations by the IRB. Please complete all checklists relevant to your research.

### I. Waivers or Alterations of Consent, Assent, and HIPAA Authorization

#### A. Partial Waiver of Consent for Screening/Recruitment

*Complete this checklist if you are requesting a partial waiver of consent so that you can review private information to identify potential subjects and/or determine eligibility prior to approaching potential subjects for consent or parental permission.*

1. Describe the data source that you need to review (e.g., medical records):  
